9.5.6 Abuse or Diversion of Study Drug

Adverse events associated with abuse or diversion will be appropriately reported as AEs and monitored per [Section 9.5.1.5.1](#). Abuse is always to be captured as an AE.

During the study, the investigator should be aware of the possibility of abuse or diversion of study drugs and should report any concern about mishandling, abuse, loss, theft, or diversion of study drugs by completing the Potential Abuse-related Medication Handling Event eCRF.

9.5.7 Confirmation of Medical Care by Another Physician

The investigator will instruct subjects to inform site personnel when they are planning to receive medical care by another physician. At each visit, the investigator will ask the subject whether he or she has received medical care by another physician since the last visit or is planning to do so in the future. When the subject is going to receive medical care by another physician, the investigator, with the consent of the subject, will inform the other physician that the subject is participating in the clinical study.

9.6 Data Quality Assurance

This study will be organized, performed, and reported in compliance with the protocol, standard operating procedures, working practice documents, and applicable regulations and guidelines. Site audits will be made periodically by the sponsor's or the CRO's qualified compliance auditing team, which is an independent function from the study team responsible for conduct of the study.

9.6.1 Data Collection

Data required by the protocol will be collected on the eCRFs and entered into a validated data management system that is compliant with all regulatory requirements. As defined by ICH guidelines, the CRF is a printed, optical, or electronic document designed to record all of the protocol-required information to be reported to the sponsor on each study subject.

Data collection on the eCRF must follow the instructions described in the CRF Completion Guidelines. The investigator has ultimate responsibility for the collection and reporting of all clinical data entered on the eCRF. The investigator or designee as identified on Form FDA 1572 (where applicable) must sign the completed eCRF to attest to its accuracy, authenticity, and completeness.

Completed, original eCRFs are the sole property of Eisai and should not be made available in any form to third parties without written permission from Eisai, except for authorized representatives of Eisai or appropriate regulatory authorities.

9.6.2 Clinical Data Management

All software applications used in the collection of data will be properly validated following standard computer system validation that is compliant with all regulatory requirements. All data, both eCRF and external data (eg, laboratory data), will be entered into a clinical system.

Electronic source (eSource) methodology may be used for some of the clinical efficacy assessments performed in this study.

9.7 Statistical Methods

All statistical analyses will be performed by the sponsor or designee. Statistical analyses will be performed using SAS software or other validated statistical software as required.

All statistical tests will be based on the 5% (2-sided) level of significance, except for the Bayesian methods on the primary endpoint.

9.7.1 Statistical and Analytical Plans

The statistical analyses of study data are described in this section. Further details of the analytical plan will be provided in the statistical analysis plan, which will be finalized before the first interim efficacy analysis.

9.7.1.1 Study Endpoints

See [Section 9.2.3](#) for a discussion of the rationale for the selection and clinical relevance of the primary study endpoint. Further information on the derived ADCOMS is described in [Section 9.5.1.3.1](#).

9.7.1.1.1 PRIMARY ENDPOINT

- Change from baseline in the derived ADCOMS at 18 months of treatment in MCI/Prodromal subjects

9.7.1.1.2 SECONDARY ENDPOINTS

Change from baseline in:

- Total hippocampal atrophy at 12 and 18 months of treatment in MCI/Prodromal subjects as measured by vMRI
- CSF A β (1-x) after 4 weeks and 18 months of treatment in MCI/Prodromal subjects
- The derived ADCOMS at 18 months of treatment in mild to moderate AD subjects (revised per Amendment 01)

9.7.1.1.3 EXPLORATORY ENDPOINTS

(revised per Amendment 01)

Change from baseline in:

- The derived ADCOMS at 12 months of treatment in MCI/Prodromal and mild to moderate AD subjects
- Total hippocampal volume at 12 and 18 months of treatment in mild to moderate AD subjects as measured by vMRI
- CSF A β (1-42) after 4 weeks and 18 months of treatment in MCI/Prodromal subjects
- CSF A β (1-x) and A β (1-42) after 4 weeks and 18 months of treatment in mild to moderate AD subjects
- The following clinical assessments at 12 weeks and at 6, 9, 12, 15, 18, 19, and 21 months: ADAS-cog, CDR, MMSE, ISLT, CBB, and FAQ in MCI/Prodromal and mild to moderate AD subjects
- CSF biomarkers of neurodegeneration (eg, tau and p-tau) at 18 months of treatment in MCI/Prodromal and mild moderate AD subjects
- Plasma and CSF amyloid, and CSF BACE1 measurements after 4 weeks and 18 months of treatment, and during posttreatment follow-up in MCI/Prodromal and mild moderate AD subjects
- Left and right hippocampal, whole brain, and total ventricular volume at 6, 12 and, 18 months in MCI/Prodromal and mild to moderate AD subjects as measured by vMRI
- Brain amyloid levels as measured by amyloid PET at 18 months in MCI/Prodromal and mild to moderate AD subjects
- The population PK parameters of E2609 including the effect of intrinsic and extrinsic factors (including *NAT2* phenotype) in MCI/Prodromal and mild to moderate AD subjects

9.7.1.2 Definitions of Analysis Sets

- The Randomized Set is the group of subjects who are randomized to study drug.
- The Safety Analysis Set is the group of subjects who receive at least 1 dose of study drug and have at least 1 postdose safety assessment.
- The Full Analysis Set (FAS) is the group of randomized subjects who receive at least 1 dose of study drug and have baseline and at least 1 postdose primary efficacy measurement.
- The Per Protocol (PP) Analysis Set is the subset of subjects in the FAS who sufficiently comply with the protocol. The PP Analysis Set will be used to conduct a sensitivity analysis of the primary efficacy endpoint. Details of the evaluability criteria will be determined before database lock and treatment unblinding, and will be specified in the statistical analysis plan.

- The PK Analysis Set is the group of subjects with at least 1 quantifiable E2609 plasma concentration accompanied by a documented dosing history.
- The PD Analysis Set is the group of subjects who have a baseline PD measurement and at least 1 posttreatment PD measurement.

9.7.1.3 Subject Disposition

The number of subjects screened, the number (percent) of subjects who failed screening, and the reasons for screen failure will be summarized, based on data reported on the Screening Disposition eCRF. The distribution of the number of randomized subjects enrolled by each site will be summarized for each randomized treatment group. The primary reasons for screen failures (did not meet inclusion or met exclusion criteria, AE, lost to follow-up, withdrawal of consent, and other) will be presented.

Study Completion: The number (percent) of randomized and treated subjects who completed the study and who withdrew from the study will be summarized according to the primary reason for discontinuation and secondary reason(s) for discontinuation, based on data reported on the Subject Disposition (Study Phase) CRF. The number (percent) will be presented by treatment group and total for subjects; randomized, not treated, treated, who completed the study, and withdrew from the study. The primary reasons for discontinuation from the study are: AE, lost to follow-up, subject choice, withdrawal of consent, pregnancy, study terminated by sponsor, and other. The secondary reasons for discontinuation from the study are: AE, subject choice, and other.

Completion of Study Treatment: The number (percent) of randomized and treated subjects who completed study drug and who discontinued from study drug will be summarized according to the primary reason for discontinuation and also according to secondary reason(s) for discontinuation, based on data reported on both the Subject Disposition (Study Phase) eCRF and ED from Study Drug eCRF. The number (percent) will be presented by treatment group and total for subjects; randomized, not treated, treated, who completed study drug, and discontinued from study drug. The primary reasons for discontinuation from the study drug are: AE, lost to follow-up, subject choice, withdrawal of consent, pregnancy, study terminated by sponsor, inadequate therapeutic response, and other. The secondary reasons for discontinuation from the study are: AE, subject choice, and other.

9.7.1.4 Demographic and Other Baseline Characteristics

Demographic and other baseline characteristics for the Safety Analysis Set and FAS will be summarized for each treatment group using descriptive statistics. Continuous demographic and baseline variables include age, MMSE and FAQ; categorical variables include sex, age group (≤ 65 years, age > 65 years), race, ethnicity, *ApoE4* status (positive or negative), prior treatment with AChEIs or memantine (no or yes), and clinical population (MCI/Prodromal AD or mild to moderate AD). (revised per Amendment 01)

9.7.1.5 Prior and Concomitant Therapy

All investigator terms for medications recorded in the eCRF will be coded to an 11-digit code using the World Health Organization Drug Dictionary (WHO DD) (Mar 2014). The number (percentage) of subjects who took prior and concomitant medications will be summarized on the Safety Analysis Set by treatment group, Anatomical Therapeutic Chemical class, and WHO DD preferred term. Prior medications will be defined as medications that stopped before the first dose of study drug. Concomitant medications will be defined as medications that (1) started before the first dose of study drug and were continuing at the time of the first dose of study drug, or (2) started on or after the date of the first dose of study drug up to the date of the last dose. All medications will be presented in subject data listings.

Medications taken within the 12-week Follow-Up period will also be recorded.

9.7.1.6 Efficacy Analyses

The MCI/Prodromal Cohort

The study in the MCI/Prodromal cohort is based on Bayesian adaptive design. Frequent interim analyses will be performed to assess the probability of early success and futility and to make early stopping decisions. Response adaptive randomization will be used to update the randomization probability among treatment groups at each interim analysis. Key definitions relevant to the Bayesian aspects of the adaptive design are given below.

Study Definitions

- **Maximum Effective Dose (d_{Max}):** The dose that achieves the greatest treatment effect.
- **ED₉₀:** The lowest dose that achieves at least 90% of the d_{Max} treatment effect in the derived ADCOMS.
- **Early Success:** The study in the MCI/Prodromal cohort will meet early success criteria if the probability that the ED₉₀ at 18 months of treatment achieves 25% improvement over placebo is at least 80%. Early success is achieved before all MCI/Prodromal subjects complete 18 months of treatment and can only be determined after at least 200 MCI/Prodromal subjects have been randomized. If early success is declared before full randomization, the randomization of new MCI/Prodromal subjects will stop but subjects already randomized into the study will receive the full 18 months of treatment (following confirmation from the Sponsor's Senior Management).
- **Futility:** The study in the MCI/Prodromal cohort will meet statistical futility criteria if the probability that the ED₉₀ is better than placebo by the clinically significant difference of 25% is less than 5% at 18 months of treatment. The statistical futility boundary is binding; if the statistical futility boundary is crossed the study will be considered to have failed.

- **Study Success:** The study in the MCI/Prodromal cohort will be considered a success if an ED₉₀ at 18 months treatment has at least an 80% probability of achieving 25% improvement over placebo at either an interim analysis or at the final analysis.

The Mild to Moderate AD Cohort (revised per Amendment 01)

All mild to moderate AD subjects will be included in the efficacy evaluations of the Mild to Moderate AD cohort. The analysis of the Mild to Moderate AD cohort is based on the group sequential design. Interim analyses in the Mild to Moderate AD cohort will only be performed after the MCI/Prodromal cohort crosses the early success boundary. The early efficacy signal based on the change from baseline of ADCOMS at 18 months is defined as crossing the interim-analysis boundaries for overwhelming efficacy in the mild to moderate AD population. The O'Brien-Fleming (OF) boundaries based on Lan-DeMets alpha spending function will be used to assess overwhelming efficacy. The corresponding OF boundaries based on *P* values will be 0.076, 0.0221, and 0.0423 for the first, second, and final analyses, respectively, according to 2 planned interim analyses at the 60% and 80% information fraction. (revised per Amendment 01)

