- **Futility:** The study in the MCI/Prodromal cohort will meet statistical futility criteria if the probability that the ED₉₀ is better than placebo by the clinically significant difference of 25% is less than 5% at 18 months of treatment. The statistical futility boundary is binding; if the statistical futility boundary is crossed the study will be considered to have failed.
- **Study Success:** The study in the MCI/Prodromal cohort will be considered a success if an ED₉₀ at 18 months treatment has at least an 80% probability of achieving 25% improvement over placebo at either an interim analysis or at the final analysis.

The Mild to Moderate AD Cohort (revised per Amendment 01): All mild to moderate AD subjects will be included in the efficacy evaluations of the Mild to Moderate AD cohort. The analysis of the Mild to Moderate AD cohort is based on the group sequential design. Interim analyses in the Mild to Moderate AD cohort will only be performed after the

MCI/Prodromal cohort crosses the early success boundary. The early efficacy signal based on the change from baseline of ADCOMS at 18 months is defined as crossing the interim-analysis boundaries for overwhelming efficacy in the mild to moderate AD population. The O'Brien-Fleming (OF) boundaries based on Lan-DeMets alpha spending function will be used to assess overwhelming efficacy. The corresponding OF boundaries based on P values will be 0.076, 0.0221, and 0.0423 for the first, second, and final analyses, respectively, according to 2 planned interim analyses at the 60% and 80% information fraction. (revised per Amendment 01)

Analysis for the primary endpoint

Primary analysis of primary endpoint

The primary analysis will be based on MCI/Prodromal subjects from the FAS with the prespecified censoring rule applied. The primary endpoint is the change from baseline to 18 months in the derived ADCOMS. The dose-response of the primary endpoint is modelled with a first-order normal dynamic linear model, where Normal and Inverse-Gamma priors are used. The primary efficacy analysis will calculate the Bayesian posterior probability that the dose identified is the most likely ED₉₀ dose that achieves 25% improvement over the placebo arm. At each interim analysis and the final analysis, 2 Bayesian probabilities will be summarized for each active dose: the probability it is the ED₉₀ dose and the probability of achieving 25% improvement over the placebo arm.

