The null and alternative hypotheses and the statistical test are the same as those for vMRI. To estimate the sample size for the amyloid PET imaging subgroup at 18 months, a common SD of the change from baseline was estimated at 0.33 and a reasonable mean difference between treatment and placebo was estimated as 0.25 (standardized uptake value ratio [SUVR]). Assuming a moderate dose-response, the best dose would achieve a difference of 0.25 (SUVR) and the middle and low doses would achieve a difference of 0.2 and 0.15 (SUVR), respectively; this would require a total of 100 subjects from all 4 arms at 18 months to achieve 80% power.

9.7.2.2 Sample Size Rationale for the Mild to Moderate AD Cohort (revised per Amendment 01)

ADCOMS at Month 18

The null hypothesis is that there is no difference between active dose and placebo. There are 2 null hypotheses corresponding to 2 active doses. The alternative hypothesis is that at least 1 null hypothesis is false. The null hypotheses will be tested using Dunnett's test with 2-sided alpha of 0.05 as described for the Mild to Moderate AD cohort in [Section 9.7.1.6.2](#). The statistical power was estimated through simulation for the dose-response assumption that the percent reduction in change from baseline of ADCOMS at 18 months compared with placebo would be 33% and 50% corresponding to the 2 doses, respectively. The estimated power for the actual planned 200 mild to moderate AD subjects is approximately 80% assuming a 2-sided alpha of 0.05. (revised per Amendment 01)

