The DSMB will continue to monitor the safety aspects of the study throughout Stage A and Stage B. Details will be provided in the DSMB Charter. The study may be stopped for safety at any time.

The first Bayesian adaptive interim analysis will be conducted when 100 MCI/Prodromal subjects have been randomized into the study (ie, including MCI/Prodromal subjects from Stage A and Stage B). (revised per Amendment 01) Further interim efficacy analyses will be conducted after each additional 50 MCI/Prodromal subjects have been randomized, to a maximum of 500 MCI/Prodromal subjects (ie, at 100, 150, 200, 250, 300, 350, 400, 450, 500 subjects randomized). If the study reaches full randomization, additional interim analyses will be conducted every 3 months until all subjects complete 18 months of treatment. The study will be monitored for futility at each interim analysis. Starting at the interim analysis for 200 subjects, the study will be monitored for success at each interim analysis. Each interim analysis will be conducted on data for the derived ADCOMS.

In addition, at each interim efficacy analysis, response adaptive randomization will be used to update the allocation of new subjects between placebo and active doses according to a predefined automated algorithm.

The Mild to Moderate AD Cohort (revised per Amendment 01)

A group sequential design will be used for the Mild to Moderate AD cohort. (revised per Amendment 01) This design includes 3 looks, 2 interim looks (when 60% and 80% information fractions are achieved) and 1 final look. The information fraction is the number of assessments in all treatment arms divided by the total number of expected assessments. Interim analyses will be performed after the MCI/Prodromal cohort crosses the early success boundary. The corresponding efficacy boundaries will be 0.076, 0.022, and 0.0423 for the first, second, and final analyses, respectively. If the actual information fraction during the interim analyses is different from 60% or 80% at the interim, the efficacy boundaries will be adjusted based on the actual information fraction.

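### The first O'Brien-Fleming boundary for the Mild to Moderate AD cohort is printed as 0.076; the stated method gives 0.0076

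*Protocol*

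**What the plan says.** Section 9.7.1.6 sets a group sequential plan for the Mild to Moderate AD cohort. It says that O'Brien-Fleming "boundaries based on Lan-DeMets alpha spending function will be used to assess overwhelming efficacy", with the levels set "according to 2 planned interim analyses at the 60% and 80% information fraction". An early efficacy signal on the 18-month ADCOMS change is defined as crossing one of the interim boundaries. The boundary P "values will be 0.076, 0.0221, and 0.0423 for the first, second, and final analyses, respectively".

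Section 9.7.3 repeats the plan: "This design includes 3 looks, 2 interim looks (when 60% and 80% information fractions are achieved) and 1 final look". It prints the levels again: "The corresponding efficacy boundaries will be 0.076, 0.022, and 0.0423 for the first, second, and final analyses, respectively". The Synopsis carries the same first figure twice, under Efficacy Analyses ("The corresponding OF boundaries based on P values will be 0.076, 0.0221, and 0.0423 for the first, second, and final analyses") and under Interim Analyses.

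The error rate is fixed in two places. Section 9.7 states that "All statistical tests will be based on the 5% (2-sided) level of significance, except for the Bayesian methods on the primary endpoint", and the sample size rationale for this cohort (Section 9.7.2.2) states that "The null hypotheses will be tested using Dunnett's test with 2-sided alpha of 0.05".

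**The concern.** O'Brien-Fleming boundaries are strict early and relax towards the end, so the nominal P-value levels must rise from look to look. The printed sequence falls from 0.076 to 0.0221 and then rises to 0.0423. Its first level is looser than the final one, and looser than the 5% allowed for the whole cohort.

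The number is a prespecified decision threshold for a secondary efficacy endpoint. Read literally, a result at the 60% look that fails even an unadjusted 5% test would be declared overwhelming efficacy, and the 5% error control would be lost.

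**Working it through.** **Inputs, all from the protocol**
- Two-sided alpha 0.05 (Sections 9.7 and 9.7.2.2).
- Lan-DeMets spending of O'Brien-Fleming type (Section 9.7.1.6).
- Looks at t = 0.60, 0.80 and 1.00 (Sections 9.7.1.6 and 9.7.3).
- Printed levels 0.076, 0.0221 and 0.0423 (Section 9.7.1.6).

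**Step 1: cumulative alpha.** Treating two-sided 0.05 as twice one-sided 0.025, the cumulative two-sided alpha is α(t) = 4[1 − Φ(z₀.₉₈₇₅/√t)], with z₀.₉₈₇₅ = 2.2414.
- t = 0.60: 2.2414/0.7746 = 2.894, so α = 0.00762
- t = 0.80: 2.2414/0.8944 = 2.506, so α = 0.02442
- t = 1.00: α = 0.05000

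**Step 2: boundaries.** The boundaries were solved by recursive numerical integration, with correlation √(tᵢ/tⱼ) between the statistics at looks i < j.

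| Look | t | z | Two-sided nominal P | Printed |
|---|---|---|---|---|
| 1 | 0.60 | 2.669 | 0.0076 | 0.076 |
| 2 | 0.80 | 2.289 | 0.0221 | 0.0221 |
| 3 | 1.00 | 2.031 | 0.0423 | 0.0423 |

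The second and third printed levels are reproduced, which confirms that this is the method the authors used. Only the first differs, by a factor of ten.

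**Step 3: could another reading give 0.076?**
- The same spending form applied once to the total two-sided 0.05: 0.0114, 0.0244, 0.0392.
- One-sided alpha 0.05, as one-sided P values: 0.0114, 0.0251, 0.0410.
- Classical O'Brien-Fleming: 0.0085, 0.0227, 0.0416.

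None comes near 0.076, and none matches the other two levels as well. More generally, the alpha spent at the first look equals its nominal level, so 0.076 cannot arise from any function whose total is 0.05.

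**Step 4: type I error.** Probability of first crossing at each look under the null:

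| Levels | Look 1 | Look 2 | Look 3 | Total |
|---|---|---|---|---|
| 0.076, 0.0221, 0.0423 | 0.0760 | 0.0041 | 0.0166 | 0.0967 |
| 0.0076, 0.0221, 0.0423 | 0.0076 | 0.0168 | 0.0256 | 0.0500 |

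With the printed levels, 0.0760 + 0.0041 = 0.0801 is already spent by the second look. If the printed levels were read as one-sided P values, the total would be 0.093. Writing 0.022 for 0.0221 at look 2 is rounding and has no practical effect: with 0.0076 at look 1 the total is 0.04996 rather than 0.05001.

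**The case against.** The arithmetic is not in dispute. The case for giving the point less weight has four parts.

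- **The method is named correctly.** A statistician who programs it will obtain 0.0076, and Section 9.7.3 requires the boundaries to be recalculated if the actual information fraction is not 60% or 80%. Real looks seldom fall exactly on plan, so the misprint would often be replaced. This helps only in part. At the planned fraction the printed figure governs. Elsewhere the analysis group would hold a recalculated value far below the protocol's own number, with the data already in hand.
- **The looks are conditional.** They occur only after the MCI/Prodromal cohort crosses its early success boundary; otherwise there is only a final analysis. This is true, and the 9.7% applies only when the looks take place. That is, however, the situation the rule was written for.
- **The endpoint is one of three secondary endpoints.** Study success rests on the MCI/Prodromal cohort, and the passages on this boundary attach no stopping action to crossing it. This limits the consequence but does not make the threshold right.
- **The version.** The statistical text is that of Amendment 01. Appendix pages marked as revised under Amendment 02 are also in the file, but the matching statistical section is not, so a later correction cannot be excluded. No text in hand gives 0.0076, and the Version 2.0 synopsis already had 0.076, so the error survived at least one revision.

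**Conclusion.** The point holds. The stated inputs give 0.0076, 0.0221 and 0.0423, so 0.076 is a misplaced decimal. Applied as printed, it raises overall two-sided type I error from 5.0% to 9.7% and lets any first-look P value between 0.0076 and 0.076 count as overwhelming efficacy, including values above 0.05.

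The 9.7% assumes that looks are taken at 60%, 80% and 100% information, that the printed levels are used without recalculation, and that one two-sided test is made at each look, for example on a Dunnett-adjusted P value. The finding is established for the Amendment 01 text.

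**What to change.** Replace 0.076 with 0.0076 in the four places that state the rule: Synopsis (Efficacy Analyses and Interim Analyses), Section 9.7.1.6 and Section 9.7.3. Write 0.0221 consistently for the second look. Add a sentence saying that if MCI/Prodromal early success does not occur and no interim look is taken in this cohort, no alpha has been spent and the single final test is at 0.05 rather than 0.0423.

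Check any later amendment, the SAP and the independent analysis group's charter for the same figure and correct it wherever it appears. This should be done before any unblinded look at the cohort. The change is to wording only: sample size, visits and procedures stay as they are, and there is no operational cost.
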